	
renal comorbidities, etc.) and relevant data (STOP-Bang Scoring Model, Berlin questionnaire, and echocardiography data)
 
 ▪ Concomitant medications for comorbidities ▪ Anti-fibrotic drug treatment: start/stop dates and dosage ▪ Adverse drug reaction (ADR) ▪ Serological test: Hct, Hb, platelets, RBC, WBC, neutrophils, lymphocytes, monocytes, eosinophils, basophils, CRP, CK, rheumatoid factor, antinuclear Ab, anti-Jo1 Ab, Sjogrens SS-A or SS-B Ab, scleroderma-70 Ab, C-ANCA, and p-ANCA, etc.. ▪ Biomarkers of IPF progression: PDGF, VEGF, FGF, etc.. ▪ Gene polymorphism testing: MUC5B, etc.. 
Primary outcomes
 
 ▪ Annual percentage of decline from baseline in FVC ▪ Annual decline from baseline in DLco ▪ Annual decline from baseline in resting and exercise SpO₂ ▪ Annual percentage of decline from baseline in TLC ▪ Annual percentage of decline from baseline in IC 
Secondary outcomes
 
 ▪ Time to first acute exacerbation of IPF after enrolment ▪ Annual change from baseline in SGRQ ▪ Annual change from baseline in CAT ▪ Annual change from baseline in 6MWT ▪ Mortality (with cause of death) and time to death
--	--

Non-interventional Study Protocol

BI Study Number 1199-0303

c16462309-02

 Proprietary confidential information © 2017 Boehringer Ingelheim International GmbH or one or more of its affiliated companies

Data sources:	Source data are collected from medical charts at 10 medical centers, the expert centers where IPF patients are mainly managed in Taiwan. Case report form will be designed for data collection.
Study size:	Approximately 100 patients are planned to be enrolled. Since most outcomes are continuous, this number should be sufficient in order to get insights into Taiwanese IPF patients.

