9.2.2 Study population

Inclusion criteria

Patients can be included if **ALL** the following criteria are met:

1. Newly diagnosed IPF within 6 months based upon recent ATS/ERS/JRS/ALAT IPF guideline (Ref 1, Raghu G, et al. 2011)

Non-interventional Study Protocol
BI Study Number 1199-0303**c16462309-02**

Proprietary confidential information © 2017 Boehringer Ingelheim International GmbH or one or more of its affiliated companies

- Exclusion of other known causes of ILD (e.g. domestic and occupational environmental exposures, connective tissue disease, and drug toxicity) which needs serological test.
 - Assessment of IPF based on HRCT or HRCT and surgical lung biopsy, if available.
2. Patient \geq 20 years of age
 3. Written informed consent prior to participation
 4. Patients with further follow-up possible with participating physician during planned study period
 5. Ability to read and write in the local language

Exclusion criteriaPatients should not be included if **ANY** of the following criteria is met:

1. Lung transplantation expected within next 6 months.
2. Inclusion in ongoing clinical trials

Withdrawal criteria

Every patient has the right to discontinue study participation at any time, and every patient may be discontinued from the study for any reason beneficial to his/her well-being. If a patient ends the study earlier, the physician must record the discontinuation/withdrawal reason on the CRF. A patient may discontinue the study participation due to any one of the following reasons:

1. Withdrawal of consent
2. Lost to follow-up
3. Administrative problems
4. Lung transplantation
5. Death

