9.2.3 Study visits

The collection of patient data should be managed during routine clinical practice visits, which is approximately every 3 month in Taiwan Information on pre-specified variables of interest will be collected at inclusion (baseline visit) and captured at pre-defined intervals during the follow-up period (e.g. at 3, 6 months (time window: \pm 1 month) and then every 6 months (time window: \pm 2 month) intervals until finalization of the study).

Data will be collected and recorded on the CRF at baseline and follow-up visits according to **Table 1 Data Collection Schedule**, if available.

Baseline visit (Visit 1)

Non-interventional Study Protocol

BI Study Number 1199-0303

c16462309-02

Proprietary confidential information © 2017 Boehringer Ingelheim International GmbH or one or more of its affiliated companies

No data collection for study purposes must be performed unless the patient has consented to participate in the study. Once the patient has signed the informed consent form, the patient is considered to be enrolled in the study and patient details should be recorded on the enrolment log.

The following procedures will be performed at the baseline visit, and data will be collected from the medical chart and recorded on the CRF, **if available**:

- Sign informed consent form. A copy of the consent should be given to the patient.
- Review of inclusion and exclusion criteria, and record date of inclusion
- Collection of demographic data: Age, gender, race, education level, environmental/occupation exposures, height, weight, and BMI
- Collection of IPF-related characteristics: High-resolution computed tomography (HRCT), surgical lung biopsy, multidisciplinary team (MDT) diagnosis, and UIP pattern
- Record of IPF symptoms at baseline
- Record of smoking status
- Collection of comorbidities and its related concomitant medications that prescribed within 6 months prior to enrolment with IPF diagnosis.
 - Collect STOP-Bang Scoring Model results to evaluate if patients have comorbidity of obstructive sleep apnea
 - Collect Berlin questionnaire results for patients with comorbidity of obstructive sleep apnea
 - Collect echocardiography results for patients with comorbidity of PH
- Record of anti-fibrotic drugs used currently and within 6 months before enrollment with IPF diagnosis (i.e., nintedanib and pirfenidone)
- Collect spirometry results that closest to the baseline
- Collect 6MWT results that closest to the baseline

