***Information to be collected on screening failures**

Non-interventional Study Protocol**BI Study Number 1199-0303****c16462309-02**

Proprietary confidential information © 2017 Boehringer Ingelheim International GmbH or one or more of its affiliated companies

The screening log entry with demographic information and the primary reason for not continuing or ineligibility must be completed for all screened patients that do not qualify for Baseline Visit (Visit 1). CRF pages of screening criteria and demographics (birth, gender, race, education level, environmental/occupation exposures, height, weight, and BMI); and the study screening log will be collected for these patients. The subject number of these ineligible patients should be kept, and the following enrolments will be numbered in sequence.

Remark: Since this is a non-interventional study, all the tests collected at baseline will be performed as judged appropriate by the treating physician, and the results of interest will be recorded only if they are available. This study does not require additional tests or examinations to be performed.

First month of follow-up period (Visit 2, Week 4)

The first time of data collection during the follow-up period will be scheduled for the first month (4 weeks after the baseline visit) with an allowed window of ± 14 days. The following assessments will be documented:

- Record of IPF symptoms
- Record of current anti-fibrotic drugs used for IPF (i.e., nintedanib and pirfenidone) and reasons and date for dose change or discontinuation
- spirometry results
- 6MWT results
- St. George's Respiratory Questionnaire (SGRQ) results
- COPD Assessment Test (CAT) results
- Record of any acute exacerbations since the baseline visit
- Conduct safety reporting for OFEV[®] relevant ADR (serious, non-serious), fatal AEs, and pregnancies; and record them on corresponding ADR forms and CRF pages

Remark: Since this is a non-interventional, observational study, all the tests collected will be performed as judged appropriate by the treating physician, however for test marked as mandatory variables it will be at least assessed if the test has been performed and if yes the results of interest will be recorded. This study does not require additional tests or examinations to be performed.

Subsequent follow-up period (Visit 3 ~ 10, Week 16 ~ 100)

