Non-interventional Study Protocol
BI Study Number 1199-0303

c16462309-02

Proprietary confidential information © 2017 Boehringer Ingelheim International GmbH or one or more of its affiliated companies

Week# Visit	Baseline	Wk 4	Wk 16	Wk 28	Wk 40	Wk 52	Wk 64	Wk 76	Wk 88	Wk 100	
	1	2	3	4	5	6	7	8	9	10	
Variables			← 3-month interval →								
Allowed window		± 14 days	← ± 1 month →								
- Berlin Questionnaire-obstructive sleep apnea ⁴	X ^{&}			X		X		X		X	
- Echocardiography data-PH	X ^{&}			X		X		X		X	
Concomitant medications ⁵	X	X	X	X	x	x	X	X	X	X	
Record of anti-fibrotic drugs*	X ⁶	X	X	X	X	X	X	X	X	X	
Lung function*, ⁷	X ^{&}	X	X	X	X	X	X	X	X	X	
6MWT*	X ^{&}					X				X	
SGRQ*	X ^{&}	X	X	X	X	X	X	X	X	X	
CAT*	X ^{&}	X	X	X	X	X	X	X	X	X	
Acute exacerbation	X	X	X	X	X	X	X	X	X	X	
Safety reporting ⁸	← →										
Serological tests*, ⁹	X ^{&}		X			X		X		X	
Biomarkers*, ¹⁰	X					X				X	
Gene test*, ¹¹	X										

*Data will be collected, if applicable. All examinations and managements will be based on the discretion of the physician and regular practice.

#Data collection time points will follow visit schedule in clinical practice.

&Since this is an observational study, examinations and tests will be performed as judged appropriately by the treating physician according to local medical standards, and the results of interest that closest to the baseline will be registered only if those are available prior to baseline visit.

- Age, gender, race, education level, environmental/occupation exposures, height, weight, and BMI.
- HRCT, surgical lung biopsy, multidisciplinary team (MDT) diagnosis, and UIP pattern.
- Cough, dyspnea, fatigue, weight loss, dizziness, chest pain, anxiety, aching muscles and joints, clubbed fingers, require oxygen therapy (device), or others (according to physicians' judgment and should be specified on the CRF)
- STOP-Bang Scoring Model data will be collected to assess if patients have obstructive sleep apnea, and Berlin questionnaire results will only be collected from those with suspected/confirmed obstructive sleep apnea according to STOP-Bang Scoring Model.
- Concomitant medications used for treating comorbidities within 6 months prior to enrolment will be collected.
- Anti-fibrotic drugs (i.e., nintedanib and pirfenidone) used within 6 months before baseline will be recorded.
- Spirometry data include FVC, DLCO, SpO₂, TLC, IC, etc.
- OFEV relevant ADR (serious and non-serious), fatal AEs, and pregnancies.

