11.2 ADVERSE EVENT AND SERIOUS ADVERSE EVENT COLLECTION AND REPORTING

The investigator shall maintain and keep detailed records of all AEs in their patient files.

Collection of AEs

The study design is of non-interventional nature and the study is conducted within the conditions of the approved marketing authorization. Sufficient data from controlled interventional trials are available to support the evidence on the safety and efficacy of the studied BI drug. For this reason, the following AE collection and reporting requirements have been defined.

The following must be collected by the investigator in the paper CRF from signing the informed consent onwards until the end of the study:

- All adverse drug reaction (ADRs) (serious and non-serious),
- All AEs with fatal outcome,

All ADRs including those persisting after study completion must be followed up until they are resolved, have been sufficiently characterized, or no further information can be obtained.

The investigator should carefully assess whether an AE constitutes an ADR using the information below.

Causal relationship of adverse event

The definition of an adverse reaction implies at least a reasonable possibility of a causal relationship between a suspected medicinal product and an adverse event. An adverse reaction, in contrast to an adverse event, is characterized by the fact that a causal relationship between a medicinal product and an occurrence is suspected.

Medical judgment should be used to determine the relationship, considering all relevant factors, including the pattern of reaction, temporal relationship, de-challenge or re-challenge, and confounding factors such as concomitant medication, concomitant diseases, and relevant history.

Non-interventional Study Protocol
BI Study Number 1199-0303**c16462309-02**

Proprietary confidential information © 2017 Boehringer Ingelheim International GmbH or one or more of its affiliated companies

Arguments that may suggest a **reasonable causal relationship** could be:

- The event is **consistent with the known pharmacology** of the drug
- The event is known to be caused by or **attributed to the drug class**.
- A **plausible time to onset of the event** relative to the time of drug exposure.
- Evidence that the **event is reproducible** when the drug is re-introduced
- **No medically sound alternative etiologies** that could explain the event (e.g. preexisting or concomitant diseases, or co-medications).

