11.5 Safety Analyses

- Frequency of adverse events and serious adverse events.
 - AEs and SAEs will be summarized as number of AEs, number of subjects with AEs and percentage of subjects with AEs. The summary will be further categorized by the seriousness, severity, causality, and outcome.
 - AE will be coded using the MedDRA dictionary. All adverse events will be classified using MedDRA terminology. The number of subjects and percentage of subjects will be computed by System Organ Class and Preferred Term to show the incidence of AE. The incidence of AE will be categorized by the severity. The incidence of AE by the severity will be presented as a separate table. Number of events and number of subject with events will be included in the summary table.
 - The incidence of AEs suspected related to nintedanib will be computed per the MedDRA terms. Number of suspected events and the number of subjects with suspected event with the corresponding percentage will be listed. The incidence of AEs suspected related to nintedanib will also be categorized by the severity.

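### The SAP's single incidence of nintedanib-suspected events pools patients observed from first dose with patients already exposed before consent, and should be split by start date

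*Protocol*

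**What the plan says.** Protocol 11.2 introduces its collection list with: "The following must be collected by the investigator in the paper CRF from signing the informed consent onwards until the end of the study". The list holds all ADRs and all adverse events with a fatal outcome. Expedited reporting in the same section uses the same window.

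Protocol 9.2.2 admits patients on this basis: "Newly diagnosed IPF within 6 months based upon recent ATS/ERS/JRS/ALAT IPF guideline". No entry criterion excludes earlier anti-fibrotic treatment, and the protocol expects it. The Visit 1 list in 9.2.3 has "Record of anti-fibrotic drugs used currently and within 6 months before enrollment with IPF diagnosis", and a footnote to Table 1 says "Anti-fibrotic drugs (i.e., nintedanib and pirfenidone) used within 6 months before baseline will be recorded".

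The Protocol abstract (section 4) defines the drug variable as "Anti-fibrotic drug treatment: start/stop dates and dosage". The reason for a change appears first in the Visit 2 list of 9.2.3: "Record of current anti-fibrotic drugs used for IPF (i.e., nintedanib and pirfenidone) and reasons and date for dose change or discontinuation". The list for Visits 3 to 10 repeats that item. Protocol 9.3.1 likewise ties the reason for an adjustment or interruption to the observational period.

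SAP 11.5 states: "The incidence of AEs suspected related to nintedanib will be computed per the MedDRA terms". Events, subjects and percentages are to be shown, also by severity. The only planned grouping is any anti-fibrotic drug versus none (SAP 8.4 and 9). SAP 10.1 counts exposure days during the study only.

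**The concern.** A patient who starts nintedanib after consent is observed for reactions from the first dose. A patient who started before consent is observed only from some later point on treatment. If the second patient had a reaction that cleared before consent, nothing in the documents asks for it, and the patient can count as event-free. If that patient stopped the drug because of a reaction, the drug record can show the stop, but the Visit 1 list does not ask why.

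SAP 11.5 puts both kinds of patient into one percentage and calls it incidence. A reader could take it as the proportion of Taiwanese patients who have a suspected reaction after starting nintedanib. The pooled figure does not estimate that unless nobody was treated before consent, or no treated patient had reactions only before consent. The limitations section (Protocol 9.9) does not mention exposure before consent.

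**Working it through.** **No figure to reproduce.** The documents state no expected ADR incidence, no share of patients on nintedanib at consent and no distribution of onset times. The check is therefore a range under stated assumptions.

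**From the documents.** ADR observation starts at consent. Follow-up is 100 weeks (Protocol 9.3.4), so T = 700 days / 30.44 = 23.0 months. Recorded use before consent reaches back up to 6 months.

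**Assumed.** Share s of nintedanib users already on drug at consent: 25%, 50% or 75%. Time m on drug before consent: 3 or 6 months. Four monthly reaction hazards, two constant and two concentrated in the first 3 months. Patients stay on drug, and reactions before consent are not seen at all.

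**Formulas.** H(t) is the cumulative hazard at time t since first dose.

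- Starting at consent: 1 − exp[−H(T)]
- Already exposed, as observed: 1 − exp[−(H(m+T) − H(m))]
- Already exposed, since first dose: 1 − exp[−H(m+T)]
- Pooled figure: (1 − s) × starting at consent + s × already exposed

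**One case in full.** Hazard 0.20 per month for 3 months, then 0.03; s = 50%; m = 3.

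- Starting at consent: H = 0.20 × 3 + 0.03 × 20.0 = 1.20, giving 69.9%.
- Already exposed, as observed: 0.03 × 23.0 = 0.69, giving 49.8%.
- Pooled, as observed: 0.5 × 69.9 + 0.5 × 49.8 = 59.9%. This is 10.0 points below patients starting at consent.
- Already exposed, since first dose: H = 0.60 + 0.69 = 1.29, giving 72.5%.
- Pooled, since first dose: 0.5 × 69.9 + 0.5 × 72.5 = 71.2%. The observed figure is 11.3 points lower.

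**All cases** (differences taken before rounding):

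| Assumed hazard per month | Starting at consent | Pooled, s = 25 / 50 / 75% | Points below patients starting at consent | Points below incidence since first dose (all s and m) |
|---|---|---|---|---|
| 0.01 constant | 20.5% | 20.5% throughout | 0 | 0.6 to 3.5 |
| 0.05 constant | 68.3% | 68.3% throughout | 0 | 1.1 to 6.2 |
| 0.20 for 3 months, then 0.03 | 69.9% | 64.9 / 59.9 / 54.8% | 5.0 / 10.0 / 15.0 | 5.7 to 18.8 |
| 0.40 for 3 months, then 0.01 | 75.3% | 61.6 / 47.9 / 34.2% | 13.7 / 27.4 / 41.1 | 13.9 to 42.2 |

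The comparator matters. Under a constant hazard, patients already exposed have the same chance of a reaction in 100 weeks as patients starting at consent, and pooling does no harm on that scale. A gap opens there only when the hazard is higher early. Measured since first dose, leaving out reactions before consent can only lower the proportion, never raise it.

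**The case against.** The plan never promises incidence since first dose. Events run from consent and SAP 10.1 counts exposure over the study, so the two windows agree and the percentage is correct for the on-study period. Safety is not among the primary or secondary outcomes, the study is not a PASS, and Protocol 11.2 gives a reason for limited event collection. Safety reporting is also a Visit 1 item, so a reaction still present at consent may be captured, which would shrink any gap. A further split of about 100 patients gives small cells, and Protocol 9.9 allows stratified analyses to be dropped for that reason.

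Most of this stands, and it limits the point to labelling and interpretation. It does not remove the point: SAP 6.2.3 makes adverse event frequency a safety endpoint, and SAP 11.5 uses the word incidence without saying that it is counted from consent. The text also leaves open how a reaction ongoing at consent is counted.

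Two stronger readings are tempting and are not supported:

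- A reader might infer that early dose changes are lost. Start and stop dates and dosage are defined variables, and use before baseline is recorded. Only the reason is unlisted at Visit 1, and the CRF itself is not among the documents.
- A reader might call this left truncation, with patients selected for tolerating the drug. Entry does not depend on being on nintedanib or tolerating it, and a patient who stopped for a reaction can still enrol. What is missing is history before entry, not the patients.

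**Conclusion.** The point holds as a weakness of reporting and interpretation. SAP 11.5 pools two kinds of observation under one label. The result is valid as a proportion with a suspected event during the study. It understates incidence since first dose to the extent that already-treated patients had reactions only before consent. Under the assumed inputs that is about 0.6 to 42 percentage points. Relative to patients starting at consent, the shortfall is zero under a constant hazard and reaches about 41 points in the most front-loaded case with 75% already treated. If nobody started before consent, there is no shortfall on either scale.

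A reader might infer that the reported incidence is simply too low. The documents do not support that: they give neither the onset pattern nor the share already treated, and the figure is right for the period it covers. Nor is a biased rate of reaction-driven stopping shown, because SAP sections 9 to 11 describe no such analysis. The primary and secondary outcomes are not affected.

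**What to change.** 1. In SAP 11.5, tabulate nintedanib-suspected events separately for patients whose first dose is on or after consent and those whose first dose is before it, using the start dates already collected. Present the first group as incidence in new users. Label the second as events after consent in patients already exposed. State whether and in which row a reaction ongoing at consent is counted.
2. In the Visit 1 anti-fibrotic item of Protocol 9.2.3, add the question on reason and date of a dose change or stop that is already asked from Visit 2, abstracted from the chart after consent.
3. Add a sentence to Protocol 9.9 that reactions resolved before consent are not captured.

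The first change needs no new data and does not depend on the second. Its cost is precision: halving a group widens its confidence interval by a factor of about √2 = 1.41. If the cells are very small, counts can be shown without intervals. The second change costs one CRF field. No test or visit is added.

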11.3 REPORTING TO HEALTH AUTHORITIES

Adverse event reporting to regulatory agencies will be done by the MAH according to local and international regulatory requirements.

12. PLANS FOR DISSEMINATING AND COMMUNICATING STUDY RESULTS

Upon study completion and finalization of the study report, the results of this non-interventional study will be submitted for publication. The rights of the investigator and of the sponsor with regard to publication of the study design or results of this study are described in the investigator contract.

ANNEX 1. LIST OF STAND-ALONE DOCUMENTS

Number	Document Reference Number	Date	Title
1	NA	11 May 2004	St. George's Respiratory Questionnaire (SGRQ)
2	NA	2009	COPD Assessment Test (CAT)
3	NA	TBD	Berlin Questionnaire
4	NA	TBD	STOP-Bang Scoring Model

